## F. Study Procedures - Outline

### 1. Pre-intervention Behavioral Visit

**Occurs:** 1-3 days prior to the pre-intervention scan visit.

**Location:** Neuropsychology of Ingestive Behavior Lab

**Duration:** 1.5 hours

**Compensation:** \$40

**Study Session Flow:**

- Consent
- FMRI screening sheet
- Height and weight
- Internal state ratings (hunger/fullness/thirst/nausea) using visual analog scales (VAS)
- Taste test & hedonic VAS
- Surveys: FFQ, BIS-15, FCI, DEBQ, IPAQ, Handedness, SPSRQ, YFAS, BIS/BAS, PFS, Demographics
- Stop signal task
- Saliva sample
- Compensation

### 2. Pre-intervention Scan Visit

**Occurs:** 1-3 days after the pre-intervention behavioral visit.

**Location:** Biomedical Research Imaging Center (BRIC)

**Duration:** 1.5 hours

**Compensation:** \$60

**Study Session Flow:**

- Pre-Scan:
  - Weight
  - Blood glucose and hba1c
  - FMRI screening sheet
  - Internal state ratings (hunger/fullness/thirst/nausea) using VAS
  - Surveys: how long since last meal, menstrual cycle (if biologically female), sleep quality rating for past 2 days
- fMRI scan
- Post-Scan:
  - Taste test & hedonic VAS
  - Compensation

**3. Intervention: Daily Beverage Consumption (21 days)**

**Occurs:** every Monday, Wednesday, and Friday starting after their pre-intervention scan visit date for 9 occurrences

**Location:** Neuropsychology of Ingestive Behavior Lab

**Duration:** 5-15 minutes

**Compensation:** \$20 at every third visit (\$60 total)

**Study Session Flow:**

- Internal state ratings (hunger/fullness/thirst/nausea) using VAS
- Begin drinking the 10oz bottle of assigned beverage
- Taste test (of assigned beverage only) & hedonic VAS
- Collection of returned empty bottles
- Distribution of next day's (or weekend's) bottles
- Compensation

**4. Post-intervention Scan Visit**

**Occurs:** 2-5 days after the end of the intervention

**Location:** Biomedical Research Imaging Center (BRIC)

**Duration:** 2 hours

**Compensation:** \$80

**Study Session Flow:**

- Pre-Scan:
  - Weight
  - Blood glucose and hba1c
  - FMRI screening sheet
  - Internal state ratings (hunger/fullness/thirst/nausea) using VAS
  - Surveys: how long since last meal, menstrual cycle (if biologically female), sleep quality rating for past 2 days
- fMRI scan
- Post-Scan:
  - Taste test & hedonic VAS
  - Compensation

**5. Post-intervention Behavioral Visit**

**Occurs:** 1-3 days after the post-intervention scan visit.

**Location:** Neuropsychology of Ingestive Behavior Lab

**Duration:** 1 hours

**Compensation:** \$60

**Study Session Flow:**

- Weight
- Internal state ratings (hunger/fullness/thirst/nausea) using visual analog scales (VAS)
- Taste test & hedonic VAS
- Ad libitum beverage distribution
- Surveys: FFQ, YFAS, BIS-15, FCI, PFS, DEBQ, IPAQ
- Stop signal task
- Compensation

**G. Study Evaluations and Measurements**

Demographics and Anthropometrics. Self-ported gender, race, and ethnicity were recorded. Height was measured to the nearest mm using a stadiometer. Weight was assessed to the nearest 0.1 kg using digital scales, with participants wearing light clothing without shoes at each assessment. BMI ( $\text{kg}/\text{m}^2$ ) was then calculated.

Intervention beverages & logos. To optimally test the hypothesized sugar-contingent neuroadaptations, the active SSB condition contained 111 kcals and 27g of sugar/10 fl oz (equivalent to the caloric and sugar density of soft drinks), and the unsweetened control beverages used in the study were similarly flavored to SSBs. In a preliminary study, we performed an evaluation of 6 differently mixed fruit flavors of beverages presented in the SSB and unsweetened versions to ensure that the selected beverages are equal in palatability and novelty across flavors. For the pilot, young adults meeting the inclusion criteria proposed here ( $n=27$ ;  $\bar{x}$  BMI =  $23.3 \pm 3.5$ ) rated the mixed fruit strawberry lemonade and mixed fruit cherry orange flavors as equally palatable across flavors, and equally willing to consume daily for 3 weeks in both the SSB and unsweetened versions ( $p's=0.77-0.99$ ). These ratings were not significant impacted by gender or BMI ( $p's=0.46-0.99$ ). Beverages did not include high fructose corn syrup or artificial sweeteners, or preservatives; they are caffeine- and texture-free and generally novel in flavor. Beverages were presented in 10 fl oz bottles (295 mL). To mimic the branding of the beverages, logos were placed on the beverages that correspond with flavors. Logos were selected to be novel, of similar visual complexity, in black and white, and convey no information beyond a unique symbol, and yet be easily distinguishable from one another.

Explicit hedonic, taste and internal state ratings assessed via visual analog scales (VAS). Explicit hedonic scales were used to evaluate characteristics of the beverages, including pleasantness, desire, sweetness, bitterness, intensity, and familiarity insight into alterations the perceptual hedonic value of the beverages. Measures of internal state: hunger, fullness, thirst, and nausea were also collected. For perceptual hedonic assessments, labeled hedonic scales and generalized labeled magnitude scales provide a ratio-like data with the ability to compare individual differences in a more sensitive way than traditional scales. The participant consumed a small amount of the beverage and completed the associated scale (e.g., pleasantness). Additionally, similar internal state scales were assessed via 200mm cross-modal visual analog scales at all assessments. Scales of all beverages (SSB, USB; both flavors) were collected on the pre- and post-intervention behavioral visits. Scales for assigned beverages only were also collected on the pre- and post-intervention scan visits.

Stop signal task (SST). The Stop-Signal Task measures motor response time, accuracy, and response inhibition. The task was performed on an iPad app where participants underwent 6 total runs at the pre-intervention behavioral visit and at the post-intervention behavioral visit. Three of these runs were of their assigned condition, where the logo of their assigned beverage

was presented and the other three runs presented the logo of the unassigned beverage (of the same flavor). The order of assigned vs. unassigned was randomized across the sample. Within each run of this task, 64 (20 “go”) trials were presented, and participants were instructed to make a speeded response to a “go” stimulus except trials when an additional “stop” signal occurs (an X presented over the logo), in which case participants were instructed to withhold their response. The beverage logos (used as the “go” stimuli) were presented in two colors, indicating that the participant was to press the right or left of the screen. This speeded reaction time establishes a prepotency to respond to the logos. There were also trials where the “go” stimulus was followed, after a variable delay, by the stop-signal where the participants were instructed to withhold their response. The onset of the stop-signal, or stop-signal delay (SSD), varied and depended on the participant’s performance, such that it is decreased after a previous failure to inhibit and increased after a previous inhibition (resulting in SSD staircases across the course of the task). Participants were instructed to react quickly but also inhibit responses on trials where the stop-signal appeared as correctly responding and inhibiting were equally important.

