### **B. Study Objectives**

**Aim 1:** Test the neurobehavioral adaptions in response to repeated intake of branded SSBs relative to unsweetened, flavored control beverages (USB).

*We hypothesize that daily SSB intake will lead to:*

- a. *increases in parietal/occipital brain response during exposure to the SSB brand;*
- b. *decreased dorsal prefrontal and hippocampal response to the SSB brand;*
- c. *reduced striatal response during receipt of the assigned SSB,*

*relative to baseline and to those who are assigned to consumed the control beverage.*

**Aim 2:** Test whether BMI mediates the neurobehavioral response patterns to the consumed beverages as a function of daily SSB intake relative to baseline and to those who are assigned to consume USB.

*We hypothesize that there will be no significant interaction, such that those individuals with elevated BMI will show no difference than those at a lower BMI in the brain adaptions described in Aim 1.*

**Aim 3:** Test the impact of repeated consumption of SSBs on behavioral responses (reaction time and response inhibition) to the beverage brands measured by the stop sign task (SST).

*We hypothesize that mean reaction time to Go trials will result in a significant interaction of group assignment (sugar vs. control) by pre-/post- daily consumption. Specifically, we hypothesize that the sugar group will show a decreased reaction time to Go trials, representing faster responses relative to the control group and baseline.*

**Aim 4:** Test the impact of repeated consumption of sugar-sweetened beverage on perceptual hedonic and taste ratings.

*We hypothesize that daily beverage intake will lead to:*

- a. *no change in pleasantness and desire ratings as a function of repeated consumption of the assigned beverages.*
- b. *an assignment (sugar vs. control) by time (pre-/post- daily consumption) interaction for desire ratings of the non-assigned beverages. Specifically, we hypothesize that there will be a decrease in desire ratings of the control beverage after having consumed a SSB daily. We expect no change in pleasantness.*

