## **Statistical Analysis Cover Page**

**Official Title: Neurobehavioral Plasticity to Regular Sugar-Sweetened Beverage Intake: An fMRI Experiment**

**NCT Number: NCT03490734**

**Document Date: January 25, 2023**

## **Statistical Analysis Plan**

### **A. Sample Size and Power**

Data collection was ended early due to COVID-19 (ending March 2020), resulting in a lower than anticipated sample size (160 vs. 230), which may impact results, specifically, measures of individual differences. As our sample was smaller than anticipated we performed a sensitivity analysis using Gpower (ver. 3.1.9.7, Heinrich Heine University Düsseldorf) for the primary hypothesis using alpha = 0.05, power of 0.80 and a total sample of 123 (accounting for missing data, incomplete data collection, etc.), and we are still able to detect effect of 0.25. Inclusion Criteria: Potential participants were eligible for the study if they had BMI scores between 18 and 34 at baseline. Exclusion Criteria: Individuals with probable current Axis I psychopathology or any fMRI contra-indicators (e.g., metal implants, braces) were excluded. Those with a probable Axis I diagnosis will be provided with treatment referral information and encouraged to seek treatment, current regular use (3 or more times a week) of psychoactive drugs (e.g., cocaine, marijuana, nicotine), regular smoking, serious medical problems (e.g., cancer, diabetes), dietary practices that do not allow for intake of intervention beverages.

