### **B. Analysis Plan**

#### *1. Primary and Secondary Outcomes*

Behavioral data analysis (stop-signal reaction time & perceptual ratings of beverages): Continuous variables from the stop signal task and the visual analogue scale (VAS) ratings were summarized by descriptive statistics (e.g., mean, SD, range, median), examined via graphical analyses (e.g. histogram, Q-Q plot) and analyzed to assess the normality of the data. Data transformation of continuous variables were used as necessary. Model assumptions and potential outliers were analyzed with various modeling diagnostics and plotting techniques. Two analytic datasets are used. Participants that provided data at baseline and follow-up are used in a completers analysis (CA). An intent-to-treat (ITT) dataset, including all participants that were consented and completed one assessment, are also used. In that analysis, missing data are addressed via multiple imputation methods. Of note, in both the CA and ITT all subjects are included independent of their adherence to the intervention.

For **Aim 3**, reaction times from the stop signal task (SST) are analyzed. Following previous standards, reaction times <50 milliseconds are excluded (occurred prior to imputation). As we are not analyzing inhibition (inhibition accuracy/SSRT), no other exclusion criteria were used. Data from pre- and post-intervention SST measures are analyzed using PROC MIXED implemented in SAS (Version 9.4, Cary, NC). All available data from those completing the pre- and post-intervention behavioral visits (separate from the scan assessments) are used in the completers analysis. All those who consented are included in the ITT analysis with missing data imputed. Outcome variables assessed via the SST task are: mean reaction time, standard deviation, go accuracy of the assigned beverage (pre-/post-intervention). Each of the outcome variables is entered into 2x2 repeated measure mixed models, including group-by-time interactions. Control variables of no interest to be included are BMI, assigned flavor, and gender. Interactions are probed for pairwise comparisons using least-squared mean comparisons, specifically of a priori contrasts of interest: between-group baseline differences and follow-up differences, and within-assignment change from pre- to post-intervention. Bonferroni-adjusted two-tailed *p*-values less than 0.05 are considered significant.

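### Aim 3 omits the randomized order of assigned- and unassigned-logo runs from its model: no bias, but a possible loss of precision

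*Protocol*

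**What the plan says.** Protocol section G (Stop signal task) states that "participants underwent 6 total runs at the pre-intervention behavioral visit and at the post-intervention behavioral visit". Three of the six runs show the logo of the assigned beverage, and three show the unassigned beverage of the same flavor. On sequence it says only: "The order of assigned vs. unassigned was randomized across the sample".

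SAP section B.1 (Aim 3) takes its outcomes from the assigned-logo runs alone: "mean reaction time, standard deviation, go accuracy of the assigned beverage (pre-/post-intervention". The model is given as: "Each of the outcome variables is entered into 2x2 repeated measure mixed models, including group-by-time interactions". The covariate list is complete and short: "Control variables of no interest to be included are BMI, assigned flavor, and gender". The planned contrasts are "between-group baseline differences and follow-up differences, and within-assignment change from pre- to post-intervention". The hypothesis in Protocol section B is that "mean reaction time to Go trials will result in a significant interaction of group assignment (sugar vs. control) by pre-/post- daily consumption".

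Run order is not mentioned in the SAP. The documents do not say whether a participant kept the same order at both visits, whether each set of three runs was consecutive, or whether order was balanced within arm.

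**The concern.** Because the outcome uses only half of the runs, the order draw decides when in the session it is measured. If the assigned-logo runs come first, reaction time is recorded while the task is still new. If they come last, it is recorded after practice, and perhaps with some fatigue. If reaction time drifts over a session, the drift adds spread between participants that has nothing to do with the beverage. It is explained by a factor the investigators randomized themselves.

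A randomized design factor left out of the model sits in the residual. What is at stake is the width of the confidence intervals and the power of the Aim 3 comparisons. Precision is worth something here, because recruitment ended at 160 instead of 230 and the sensitivity analysis in SAP section A assumes 123.

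**Working it through.** **The plan's own figure.** SAP section A uses "alpha = 0.05, power of 0.80 and a total sample of 123" and reports a detectable effect of 0.25 for the primary hypothesis, without naming the metric. Read as Cohen's f for two groups, the noncentrality is 0.25² × 123 = 7.69 on 1 and 121 degrees of freedom. Power is 78.5%, and the f detectable at 80% power is 0.255. The figure therefore reproduces under that reading. It is not specific to Aim 3 and does not involve run order. I take only N = 123 from it, as 61.5 per arm, and assume it applies to Aim 3.

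**Assumed inputs** (the documents give none of these):
- d: difference between assigned-logo runs done first and done last, 0.2 to 0.5 SD, half the participants in each order
- r: pre/post correlation, 0.5 to 0.8
- runs in two consecutive blocks of three

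**Formulas.** Code order ±0.5 and set the variance at one visit, apart from order, to 1. The change then has variance 2(1−r). The share of error variance due to order is:
- one visit: 0.25d² / (1 + 0.25d²)
- change, order kept, effect falling by a fraction s between visits: 0.25(sd)² / (2(1−r) + 0.25(sd)²)
- change, order redrawn at each visit: 0.5d² / (2(1−r) + 0.5d²)

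For an effect sized to give 80% power once order is in the model, power without order is about Φ(2.802/√V − 1.960), where V is the variance inflation.

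| Comparison | Low end (d = 0.2, r = 0.5) | High end (d = 0.5, r = 0.8) | Power without order |
|---|---|---|---|
| Between-group, one visit, effect present | 0.01/1.01 = 1.0% | 0.0625/1.0625 = 5.9% | 79.6% to 77.6% |
| Interaction, order kept, equal effect (s = 0) | 0 | 0 | 80% |
| Interaction, order kept, effect halves (s = 0.5) | 0.0025/1.0025 = 0.2% | 0.0156/0.4156 = 3.8% | 79.9% to 78.5% |
| Interaction, order kept, effect disappears (s = 1) | 0.01/1.01 = 1.0% | 0.0625/0.4625 = 13.5% | 79.6% to 74.1% |
| Interaction, order redrawn | 0.02/1.02 = 2.0% | 0.125/0.525 = 23.8% | 79.2% to 68.6% |

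The rows are alternatives and must not be combined freely. If the effect disappears by follow-up, the follow-up contrast gains nothing. If it halves, the follow-up share is 0.0025/1.0025 = 0.2% to 0.0156/1.0156 = 1.5%, not 1-6%.

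**Blocking.** With blocks, the mean position of the assigned-logo runs is 2 or 5, with variance 2.25. If all 20 sequences of the six runs are equally likely, the variance is (35/12)/3 × 3/5 = 0.58, or 26% of the blocked value. If the logos alternate, the mean is 3 or 4, with variance 0.25, or 11%. Under a linear drift the variance added by order shrinks to those fractions. The 23.8% case becomes 0.0324/0.4324 = 7.5% or 0.0139/0.4139 = 3.4%.

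**Simulation check** (10,000 runs, r = 0.5, 0.5 SD order effect of equal size at both visits). With order redrawn, power for the interaction was 74.6% without order in the model and 79.6% with it. With order kept, it was 79.9% and 78.8%, which is no gain. With no group effect and no order term, the rejection rate was 0.0495 (kept) and 0.0488 (redrawn).

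**The case against.** The strongest case against acting is that the Aim 3 hypothesis is the interaction. If each participant kept one order and its effect was the same at both visits, it cancels from the pre/post change and there is nothing to recover. The covariates the SAP does list are principled: BMI and gender are stratification factors, and flavor is a tier of the randomization. No effect size, correlation or blocking scheme is documented, and practice and fatigue could partly offset each other. This all stands. It makes the gain conditional and probably small. It does not make it zero, because the documents establish neither condition for cancellation, and the SAP also names between-group contrasts at single visits.

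Two stronger readings are tempting and fail:
- **A reader might infer that order effects necessarily remain in the error of the group-by-time test.** That would need order to have been redrawn, or its effect to have changed between visits. The documents state neither. Nothing in them shows that learning is stronger at the first visit.
- **A reader might infer bias from a chance imbalance of order between arms.** With 61.5 per arm, the between-arm difference in the share doing assigned runs first has SD √(2 × 0.25/61.5) = 0.09. A 95% range of ±0.18 times 0.5 SD is up to 0.09 SD, against a standard error of √(2/61.5) = 0.18 SD for a single-visit contrast. This chance variation is already covered by the ordinary p-value, as the simulated rejection rates show.

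**Conclusion.** The point stands as a minor, precision-only improvement. Run order was randomized, it determines when the outcome is measured, and it is absent from the Aim 3 model. The omission leaves the test valid.

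For the interaction, the possible loss runs from nothing to a substantial share of error variance. It becomes material only with a large order effect, near 0.5 SD, combined with redrawn orders or an effect that fades between visits. The single-visit contrasts lose little at most, and only at a visit where the effect is present. Which case applies cannot be settled from the documents. All sizes rest on the assumed effect, correlation and blocking, and interleaved runs would cut them sharply. They are in SD units of whichever outcome is analyzed. The assumed effect was chosen with mean reaction time in mind and may not carry over to reaction-time variability or go accuracy.

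**What to change.** State in SAP section B.1 whether order was kept or redrawn between visits and whether the runs were blocked. Then add run order and order-by-time as fixed effects to the three Aim 3 mixed models, using the order in force at each visit. Code order as first or last if the runs were blocked, and otherwise as the mean position of the assigned-logo runs. If Aim 3 results are already known, keep the planned model as the main analysis and report the order-adjusted model as a sensitivity analysis. If order is left out, give the reason.

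The cost is about two degrees of freedom out of about 120. Because order was randomized, adjusting for it cannot confound the group effect. There are two practical conditions. Order must be retrievable from the task files, which the documents do not confirm. The ITT dataset also needs a simple rule for participants who missed a visit: if order was kept, carry over the order from the visit attended; if it was redrawn, generate the missing order by the same random rule within each imputation.

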#### Eating Attitudes

The Dutch Eating Behavior Questionnaire (DEBQ; 26) is a 46-item questionnaire with three subscales measuring restrained, external, and emotional eating. Responses are recorded on a 5-point Likert scale. These three scales demonstrated strong internal consistency (Cronbach’s alpha = 0.80 – 0.95), interrelationships between scales, and factorial validity.

#### Food Craving

The Food Craving Inventory (FCI) will assess the degree of craving for high- and low-fat/sugar foods (27). This scale has shown internal consistency ( $\alpha = .93$ ), 2-week test-retest reliability ( $r = .86$ ), and sensitivity to detecting change.

#### Hedonic Impact of Food Environment

The Power of Food scale assesses reported appetitive drive, food reward responsivity, sensitivity to food cues in the environment, and the frequency of food-related thoughts (35). The 21-item scale prompts subjects to rate how much they agree with statements about hedonic hunger on a 5-point scale, where 1=do not agree at all, 2=agree a little, 3=agree somewhat, 4=agree, and 5=strongly agree. The scale has strong internal consistent (Cronbach’s alpha = 0.91) and an adequate four-month test-retest reliability ( $r = .77$ ).

#### Self-report Impulsivity

The Barratt Impulsivity Scale (BIS-15) is a 15-item self-report assessment that will measure attentional, motor, and non-planning impulsivity (28). This scale has shown internal consistency ( $\alpha = .81$ ), 2-week test-retest reliability ( $r = .88$ ), and discriminates between psychiatric patients and controls.

